## LIST OF ABBREVIATIONS

AE	Adverse Event
ALT	Alanine Aminotransferase
ANC	Absolute Neutrophil Count
aPTT	Activated Partial Thromboplastin Time
AST	Aspartate Aminotransferase
BUN	Blood Urea Nitrogen
CBC	Complete Blood Count
CMP	Comprehensive Metabolic Panel
CNS	Central Nervous System
CR	Complete Response
CrCL	Creatinine Clearance
CT	Computed Tomography
CTCAE	Common Terminology Criteria for Adverse Events
DLT	Dose Limiting Toxicity
DSMB	Data and Safety Monitoring Board
D 5 W	Dextrose % in Water
DNA	Deoxyribonucleic acid
ECOG	Eastern Cooperative Oncology Group
EMR	Electronic Medical Record
eCRF	Electronic Case report form
FOCBP	Females of Child-Bearing Potential
5-FU	5-Fluorouracil
HER2	Epidermal Growth Factor receptor 2
IV (or iv)	Intravenously
ITIM	Immunoreceptor Tyrosine –based Inhibition Motif
IHC	Immuno-Histochemical
INR	International Normalized ratio
irRECIST	Immune-related Response Evaluation Criteria in Solid Tumors
LLN	Low Limit of Normal
MTD	Maximum Tolerated Dose
MBC	Metastatic Breast Cancer
MEL	Melanoma3
mAB	Monoclonal Antibody
NCI	National Cancer Institute
NS	Normal Saline
ORR	Overall Response Rate or Objective Response Rate
OS	Overall Survival
PD-1	Programmed Death -1-Ligand
PD	Progressive Disease
PFS	Progression Free Survival
PK	Pharmacokinetics
PO (or p.o.)	Per os/by mouth/orally
PR	Partial Response

PT	Prothrombin Time
RNA	Ribonucleic acid
SAE	Serious Adverse Event
SD	Stable Disease
SGOT	Serum Glutamic Oxaloacetic Transaminase
SPGT	Serum Glutamic Pyruvic Transaminase
TNBC	Triple Negative Breast Cancer
TILs	Tumor Infiltrating Lymphocytes
Q2W	Every 2 weeks
Q3W	Every 3 weeks
ULN	Upper Limit of Normal
UPIRSO	Unanticipated problem involving risk to subjects or others
WBC	White Blood Cells

## STUDY SCHEMA

**NU Study Number:** NU 16B08  
**Other Study Number:** TBD

**STUDY SUMMARY**

Title	Phase II study of Pembrolizumab and Capecitabine for advanced triple negative and hormone-refractory breast cancer.
Study Design	This is an open-label, single arm, Phase II study of the combination of pembrolizumab and capecitabine in locally advanced or metastatic Triple Negative (TNBC) and hormone-refractory Breast Cancer.
Study Center(s)	Northwestern University – Robert H. Lurie Comprehensive Cancer Center.(RHLCCC)
Objectives	
Primary objective(s):                  To evaluate the median progression-free survival (median PFS) for participants receiving pembrolizumab with capecitabine for the treatment of locally advanced or metastatic TNBC and hormone-refractory MBC.
 
Secondary Objectives:                  -The objective response rate (ORR) for participants receiving pembrolizumab with capecitabine for the treatment of locally advanced or metastatic TNBC and hormone-refractory MBC.
 
-To assess Safety and tolerability for the combination of pembrolizumab and capecitabine for the treatment of locally advanced or metastatic TNBC and hormone-refractory MBC.

Diagnosis & Key Eligibility Criteria	
Key Inclusion criteria:
 
1)The target population for this study is:
 
 
• Patients( both female and male).with triple negative locally advanced or metastatic (stage IV) breast cancer
 
• Patients with hormone refractory negative locally advanced or metastatic (stage IV) breast cancer.
 
• Patients must be ≥18 years and have a life expectancy of ≥ 90 days.
 
• Patients with central nervous system (CNS) involvement may participate if they meet all the following criteria:                         
 
• At least 4 weeks from prior therapy completion (including radiation and/or surgery) to starting the study treatment,
 
• Clinically stable with respect to the CNS tumor at the time of screening
 
 
 
 
Key Exclusion criteria:
 
 
• Patients with documented HER2-positive metastatic disease are not eligible, even if their primary breast cancer was HER2-negative.
 
• History of autoimmune disease, including but not limited to myasthenia gravis, myositis, autoimmune hepatitis, systemic lupus erythematosus
 
• Patients who have evidence of active, noninfectious pneumonitis or have a history of severe pneumonitis that required treatment with steroids are not eligible for this study.
 
• Patients with impaired GI function or GI disease that may significantly alter absorption of oral capecitabine.
 

**NU Study Number:** NU 16B08  
**Other Study Number:** TBD

Treatment Plan
	
This will be an open-label, single-arm, II study of the combination of pembrolizumab and capecitabine in locally advanced and metastatic triple negative and hormone-refractory breast cancer.
 
Pembrolizumab will be administered at 200mg IV on Day 1 of each cycle (1 cycle=21 days). Capecitabine will be administered at 1000 mg/m^2 BID D1-14 q21d. Patients will be instructed to take the morning dose of capecitabine before coming to clinic for pembrolizumab infusion. Patients will continue to receive treatment until disease progression or unacceptable toxicity. After discontinuation of study drugs, patients will be assessed every 3 months up to 1 year for PFS, with visits and/or phone calls.


Statistical Methodology
	
For PFS, assumptions are that the addition of pembrolizumab will increase PFS to 5 months compared to historical control of 3 months. Assuming exponential survival, with 27 evaluable patients, there is 80% power to detect this difference using a one-tailed z test at p<0.05.
 
Recruitment will last approximately 30 months (2.5 years) and participants will be followed for a maximum of 2 years. The primary outcomes chosen is PFS based on mechanism of action. A total of 30 patients may be accrued in order to achieve 27 evaluable patients.

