## **1.0 INTRODUCTION – BACKGROUND & RATIONALE**

### **1.1 Disease Background**

#### **1.1.1 Overview on Breast Cancer**

Approximately 231,840 women will be diagnosed with breast cancer in the United States in 2015 making it the most frequently diagnosed cancer (excluding skin cancer) in women and ranking second as a cause of cancer death. Triple negative breast cancer (TNBC), defined as estrogen receptor negative, progesterone receptor negative and human epidermal growth factor receptor 2 (HER2) negative, accounts for 9-21% of newly diagnosed breast cancers. TNBC is associated with more aggressive disease both histologically and clinically. Patients with TNBC have a lower relapse free survival and decreased overall survival (OS) when compared to hormone receptor positive disease. In an observation study conducted by Pogoda(13), metastatic disease occurred in 35% of all TNBC patients within 6 years of diagnosis.

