**1.2.2 Capecitabine**

Capecitabine is an oral fluoropyrimidine approved for treatment of metastatic breast cancer. Capecitabine is metabolized to 5-FU by an enzymatic process catalyzed by thymidine phosphorylase which has higher activity in tumor tissue compared to normal tissue. A phase II trial by Blum et al demonstrated safety and efficacy of capecitabine in patients with paclitaxel refractory metastatic breast cancer with an overall response rate of 20% and a median duration of response of 8.1 months. Another phase II study of capecitabine monotherapy in patients with both anthracycline and taxane pretreated metastatic breast cancer demonstrated an overall response rate of 28% and median time to progression of 4.9months. Capecitabine has been associated with a favorable risk-benefit profile without having a negative impact on quality of life in patients with metastatic breast cancer. Given the favorable safety profile and relative ease of administration, capecitabine is an ideal agent for consideration of combination therapy for palliative management of metastatic triple negative breast cancer. Currently, there is no randomized control data suggesting survival benefit to combined chemotherapy with capecitabine and the added chemotherapy comes with the risk of additional toxicity.

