## 2.0 OBJECTIVES

### 2.1 Primary objective(s):

- To evaluate the median progression-free survival (median PFS) for participants receiving pembrolizumab with capecitabine for the treatment of locally advanced or metastatic TNBC and hormone-refractory MBC. This will be assessed by using RECIST 1.1 criteria.

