**QualTek Molecular Laboratories**  
**MISP Receiving**  
**[name]**  
**[name]**  
**[contact]**  
**Email: [[contact]](mailto:[contact])**

## 10.0 STATISTICAL CONSIDERATIONS

For PFS, assumptions are that the addition of pembrolizumab will increase PFS to 5  
months compared to historical control of 3 months. Assuming exponential survival, with  
27 evaluable patients, there is 80% power to detect this difference using a one-  
tailed z test at  $p < 0.05$ .

Recruitment of 30 participants to accrue 27 evaluable will last approximately 30 months  
(2.5 years) and participants will be followed for a maximum of 2 years from enrollment of  
the last patient. The primary outcomes chosen is PFS based on mechanism of action..

PFS will be analyzed using a Kaplan-Meier curve. A confidence interval for the median  
PFS will be calculated (Brookmeyer, R. and Crowley, J. (1982), "A Confidence Interval for  
the Median Survival Time," *Biometrics*, 38, 29-41.), and if the confidence interval is  
totally above 3 months, then it may be concluded that the PFS exceeds 3 months.

Objective response rate will be summarized using a proportion and an exact 95% binomial confidence interval. Anti-tumor activity will be reported as a percentage change in the sum of the dimensions of all measurable lesions as defined by RECIST 1.1 criteria. The baseline imaging before treatment will be compared to each subsequent imaging assessment. The maximum anti-tumor activity will be reported using the assessment with the smallest sum of dimensions (maximum response).

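### Does an unsourced 3-month control, beside a cited 4.9 months on capecitabine alone, undermine the primary conclusion?

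*Combined protocol and SAP*

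**What the plan says.** The Study Summary (Statistical Methodology) and Section 10.0 share one design statement: "assumptions are that the addition of pembrolizumab will increase PFS to 5 months compared to historical control of 3 months". With exponential survival and 27 evaluable patients, "there is 80% power to detect this difference" by a one-tailed z test at the 0.05 level. Neither place gives a citation, population or treatment for the 3-month figure.

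The decision rule is in Section 10.0. A Brookmeyer-Crowley confidence interval for the median is calculated and, if it is "totally above 3 months, then it may be concluded that the PFS exceeds 3 months". The confidence level and any transformation are not given.

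The primary objective in Section 2.1 is "To evaluate the median progression-free survival (median PFS) for participants receiving pembrolizumab with capecitabine". It names no comparator.

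Section 1.2.2 describes two trials of capecitabine alone. One, in disease pretreated with anthracycline and taxane, reported an "overall response rate of 28% and median time to progression of 4.9months". The other, in paclitaxel-refractory disease, reported an "overall response rate of 20% and a median duration of response of 8.1 months". The 8.1 months is duration of response, so 4.9 months is the only time to progression on capecitabine alone. Section 1.1.1 adds that "TNBC is associated with more aggressive disease both histologically and clinically".

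**The concern.** The design statement credits the gain from 3 to 5 months to adding pembrolizumab, so the natural control is capecitabine alone. With no concurrent arm, the 3 months stands in for that control. It has no source, and the one relevant figure in the background nearly equals the target.

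If capecitabine alone gave a median well above 3 months in the enrolled patients, the criterion could be met with no contribution from pembrolizumab. A reader might then take a median PFS above 3 months as confirmation of the assumed gain.

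**Working it through.** **Inputs.** Null median 3 months, target 5 months, n = 27, one-sided 0.05 (Study Summary; Section 10.0). Capecitabine-alone time to progression 4.9 months (Section 1.2.2). Scans every 9 weeks (Section 5.0, footnote 2; Section 6.3.3). Assumptions: exponential times, all 27 patients observed to progression, and 95% and 90% intervals both tried because the level is not stated.

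**The plan's own power.** For a z test on the log median, power = Φ(√27 × ln(5/3) − 1.645) = 84%. Events needed for 80% power: [(1.645 + 0.842)/ln(5/3)]² = 23.7, so 24. The stated 80% is not matched exactly but is conservative for this test. The concern does not depend on the difference.

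**The z test with no pembrolizumab effect.** The test rejects 3 months once the observed median passes 3 × exp(1.645/√27) = 4.12 months. The chance of rejection at a true median m is Φ(√27 × ln(m/3) − 1.645).

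**The Section 10 rule with no pembrolizumab effect.** Without censoring, the lower limit exceeds 3 months when enough of the 27 patients are progression-free at 3 months. The untransformed interval needs at least 19 (95%) or 18 (90%). The log-log version needs 20 or 19. Each patient is progression-free at 3 months with probability S(3) = 2^(−3/m), so the chance is a binomial tail.

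| True median m (months) | S(3) | Untransformed, 95% to 90% | Log-log, 95% to 90% | z test |
|---|---|---|---|---|
| 3.0 | 0.500 | 3% to 6% | 1% to 3% | 5% |
| 3.5 | 0.552 | 8% to 16% | 4% to 8% | 20% |
| 4.0 | 0.595 | 17% to 29% | 9% to 17% | 44% |
| 4.5 | 0.630 | 28% to 43% | 16% to 28% | 68% |
| 4.9 | 0.654 | 37% to 53% | 23% to 38% | 82% |
| 5.0 | 0.660 | 40% to 56% | 25% to 40% | 84% |

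The last two rows barely differ. Neither analysis separates the cited monotherapy figure from the target. The z-test column belongs to the sample-size calculation; the interval columns describe the stated decision rule.

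**Sensitivity to scan timing.** The table treats progression as seen when it happens. If it is dated only at scans, the estimate at 3 months is the fraction progression-free at week 9 (63 days, 2.07 months): S = 2^(−2.07/m). At m = 3.0 this is 0.620, and the untransformed chances become 25% (95%) and 39% (90%). At m = 4.9 it is 0.746, giving 77% and 88%. The rule that only patients completing three cycles are evaluable is not modelled either. The table is therefore illustrative. Scan timing and evaluability are separate matters from the source of the 3 months.

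**What reading the result against 4.9 months would give.** The untransformed lower limit must exceed 4.9, with S(4.9) = 2^(−4.9/m). At a true median of 5, S = 0.507 and the chance is 3% (95%) or 7% (90%). At a true median of 8 it is 37% or 53%. On an exponential approximation, a 95% interval excludes 4.9 only when the observed median exceeds 4.9 × exp(1.96/√27) = 7.1 months.

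**The case for a change.** The strongest case for a change is that it would be cheap and that the weakness is avoidable. Any single-arm trial is exposed to a control value set too low, but not every protocol cites a monotherapy figure that nearly equals its own target and then leaves it unexplained. A few sentences in Section 10 could justify 3 months, address 4.9, and say that the result does not isolate pembrolizumab. The general remark about triple-negative disease is never tied to 3 months, and the trial also enrols hormone-refractory patients, whom that remark does not cover.

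The factual part stands: there is no source, and the two figures are not reconciled. It does not show that 3 months is wrong. The 4.9 months is time to progression, not PFS, and comes from a different population. The other capecitabine trial cited had a lower response rate, 20% against 28%. Several features of the protocol are compatible with a lower control: median survival below one year (Section 1.3), ECOG status up to 2 and stable CNS disease allowed (Section 3.1), and no stated limit on prior lines (Sections 3.1 and 3.2).

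The possible additions also gain little. A citation would record a rationale but leave the test, sample size and result as they are. A sentence limiting the claim would largely repeat Section 10, which goes no further than PFS above 3 months. A supportive reading against 4.9 months would use an unmatched figure and would almost always be inconclusive at the target, which could be mistaken for failure.

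**Conclusion.** No change is needed. The 3-month control lacks a stated source and is not reconciled with the 4.9 months in Section 1.2.2. That is a gap in justification, not a demonstrated error in the number or the rule. Pembrolizumab's addition enters only as a sample-size assumption; the objective and the decision rule concern PFS on the combination. Followed as written, the plan yields a statement about PFS above 3 months, whose truth does not depend on where 3 months came from.

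The limit on interpretation is real. If capecitabine alone gave 4.9 months, the criterion would be met in about 37% to 53% of trials with no pembrolizumab effect (untransformed interval, 27 uncensored exponential patients, continuous observation), and in about 77% to 88% if progression is dated at the 9-week scans. These figures depend on a control median that the documents do not establish for the enrolled population. An analyst reporting this single-arm trial would ordinarily state that the result does not isolate the contribution of pembrolizumab.

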## **1.0 INTRODUCTION – BACKGROUND & RATIONALE**

### **1.1 Disease Background**

#### **1.1.1 Overview on Breast Cancer**

Approximately 231,840 women will be diagnosed with breast cancer in the United States in 2015 making it the most frequently diagnosed cancer (excluding skin cancer) in women and ranking second as a cause of cancer death. Triple negative breast cancer (TNBC), defined as estrogen receptor negative, progesterone receptor negative and human epidermal growth factor receptor 2 (HER2) negative, accounts for 9-21% of newly diagnosed breast cancers. TNBC is associated with more aggressive disease both histologically and clinically. Patients with TNBC have a lower relapse free survival and decreased overall survival (OS) when compared to hormone receptor positive disease. In an observation study conducted by Pogoda(13), metastatic disease occurred in 35% of all TNBC patients within 6 years of diagnosis.

#### **1.1.2 Treatment Options for Metastatic Triple Negative Breast Cancer and Hormone-Refractory Metastatic Breast Cancer**

Current treatment options for metastatic breast cancer (MBC) are not curative and therapy aims to prolong survival while minimizing toxicity to preserve or improve quality of life for patients. In TNBC, there are no approved biologic or targeted agents and chemotherapy is the standard of care. While combination chemotherapy can provide higher rate of objective response and longer time to progression, it is associated with higher toxicity and minimal survival benefit. Current recommendations for single agent therapies include anthracyclines, taxanes, anti- metabolites and microtubule inhibitors. Ultimately, patients will develop resistance to these therapies. Similarly, patients with hormone-positive metastatic breast cancer eventually become resistant to endocrine therapy, and chemotherapy is the standard of care.

#### **1.1.3 The Immune System and Breast Cancer**

The importance of intact immune surveillance in controlling outgrowth of neoplastic transformation has been known for decades. Accumulating evidence shows a correlation between tumor-infiltrating lymphocytes (TILs) in cancer tissue and favorable prognosis in various malignancies. In particular, the presence of CD8+ T-cells and the ratio of CD8+ effector T-cells / FoxP3+ regulatory T-cells seems to correlate with improved prognosis and long-term survival in many solid tumors.

The Programmed Death-1-Ligand (PD-1 receptor-ligand) interaction is a major pathway hijacked by tumors to suppress immune control. The normal function of PD-1, expressed on the cell surface of activated T- cells under healthy conditions, is to down-modulate unwanted or excessive immune responses, including autoimmune reactions. PD-1 (encoded by the gene *Pdcd1*) is an Ig superfamily member related to CD28 and CTLA-4 which has been shown to negatively regulate antigen receptor signaling upon engagement of its ligands (PD-L1 and/or PD-L2). The structure of murine PD-1 has been resolved. PD-1 and family members are type I transmembrane glycoproteins containing an Ig Variable-type (V-type) domain responsible for ligand binding and a cytoplasmic tail which is responsible for the binding of signaling

**NU Study Number:** NU 16B08  
**Other Study Number:** TBD

molecules. The cytoplasmic tail of PD-1 contains 2 tyrosine-based signaling motifs, an immunoreceptor tyrosine-based inhibition motif (ITIM) and an immunoreceptor tyrosine-based switch motif (ITSM). Following T-cell stimulation, PD-1 recruits the tyrosine phosphatases SHP-1 and SHP-2 to the ITSM motif within its cytoplasmic tail, leading to the dephosphorylation of effector molecules such as CD3 $\zeta$ , PKC $\theta$  and ZAP70 which are involved in the CD3 T-cell signaling cascade. The mechanism by which PD-1 down modulates T-cell responses is similar to, but distinct from that of CTLA-4 as both molecules regulate an overlapping set of signaling proteins. PD-1 was shown to be expressed on activated lymphocytes including peripheral CD4+ and CD8+ T-cells, B-cells, T regs and Natural Killer cells. Expression has also been shown during thymic development on CD4-CD8- (double negative) T-cells as well as subsets of macrophages and dendritic cells. The ligands for PD-1 (PD-L1 and PD-L2) are constitutively expressed or can be induced in a variety of cell types, including non-hematopoietic tissues as well as in various tumors. Both ligands are type I transmembrane receptors containing both IgV- and IgC-like domains in the extracellular region and contain short cytoplasmic regions with no known signaling motifs. Binding of either PD-1 ligand to PD-1 inhibits T-cell activation triggered through the T-cell receptor. PD-L1 is expressed at low levels on various non-hematopoietic tissues, most notably on vascular endothelium, whereas PD-L2 protein is only detectably expressed on antigen-presenting cells found in lymphoid tissue or chronic inflammatory environments. PD-L2 is thought to control immune T-cell activation in lymphoid organs, whereas PD-L1 serves to dampen unwarranted T-cell function in peripheral tissues. Although healthy organs express little (if any) PD-L1, a variety of cancers were demonstrated to express abundant levels of this T-cell inhibitor. PD-1 has been suggested to regulate tumor-specific T-cell expansion in subjects with melanoma (MEL). This suggests that the PD-1/PD-L1 pathway plays a critical role in tumor immune evasion and should be considered as an attractive target for therapeutic intervention.

## 1.2 Intervention Background & Overview

### 1.2.1 Pembrolizumab

Pembrolizumab is a potent and highly selective humanized monoclonal antibody (mAb) of the IgG4/kappa isotype designed to directly block the interaction between PD-1 and its ligands, PD-L1 and PD-L2. Keytruda™ (pembrolizumab; MK-3475) has recently been approved in the United States for the treatment of patients with unresectable or metastatic melanoma and disease progression following ipilimumab and a BRAF inhibitor, if BRAF V600 mutation positive.

In Oct. 2015, the U.S. Food and Drug Administration granted accelerated approval for Keytruda (pembrolizumab) to treat patients with advanced (metastatic) non-small cell lung cancer (NSCLC) whose disease has progressed after other treatments and with tumors that express a protein called PD-L1. Keytruda was approved for use with a companion diagnostic, the PD-L1 IHC 22C3 pharmDx test, the first test designed to detect PD-L1 expression in non-small cell lung tumors.

An open-label Phase I trial (Protocol 001) is being conducted to evaluate the safety and clinical activity of single agent MK-3475. The dose escalation portion of this trial evaluated three dose levels, 1 mg/kg, 3

**NU Study Number:** NU 16B08  
**Other Study Number:** TBD

mg/kg, and 10 mg/kg, administered every 2 weeks (Q2W) in subjects with advanced solid tumors. All three dose levels were well tolerated and no dose-limiting toxicities were observed. This first in human study of MK-3475 showed evidence of target engagement and objective evidence of tumor size reduction at all dose levels (1 mg/kg, 3 mg/kg and 10 mg/kg Q2W). No MTD has been identified to date. 10.0 mg/kg Q2W, the highest dose tested in PN001, will be the dose and schedule utilized in Cohorts A, B, C and D of this protocol to test for initial tumor activity. Recent data from other clinical studies within the MK-3475 program has shown that a lower dose of MK-3475 and a less frequent schedule may be sufficient for target engagement and clinical activity.

PK data analysis of MK-3475 administered Q2W and every 3 weeks (Q3W) showed slow systemic clearance (0.22L/day), limited volume of distribution (7.7L), and a long half-life (26 days) (refer to Package Insert). Pharmacodynamic data (IL-2 release assay) suggested that peripheral target engagement is durable (>21 days). This early PK and pharmacodynamic data provides scientific rationale for testing a Q2W and Q3W (dosing schedule).

A population pharmacokinetic analysis has been performed using serum concentration time data from 476 patients. Within the resulting population PK model, clearance and volume parameters of MK-3475 were found to be dependent on body weight. The relationship between clearance and body weight, with an allometric exponent of 0.59, is within the range observed for other antibodies and would support both body weight normalized dosing or a fixed dose across all body weights. MK-3475 has been found to have a wide therapeutic range based on the melanoma indication. The differences in exposure for a 200 mg Q3W fixed dose regimen relative to a 2 mg/kg Q3W body weight based regimen were well within the established exposure margins of 0.5 – 5.0 for MK-3475 in the melanoma indication. The exposure margins are based on the notion of similar efficacy and safety in melanoma at 10 mg/kg Q3W vs. 2 mg/kg Q3W (i.e. 5-fold higher dose and exposure). The population PK evaluation revealed that there was no significant impact of tumor burden on exposure. In addition, exposure was similar between the NSCLC and melanoma indications.

The KEYNOTE-012 trial is a phase Ib study of patients with metastatic triple-negative breast cancer with tumors positive for the expression of PD-L1. 32 patients were treated with pembrolizumab at 10mg/kg Q2W until progression of disease. Preliminary analysis of the data demonstrated an overall response rate of 18.5% including one complete response (3.7%), four partial responses (14.8%) and seven patients with stable disease (25.9%).

